7 RISKS AND BENEFITS OF THE INVESTIGATIONAL DEVICE AND CLINICAL INVESTIGATION

The investigational device used in the study is the MONO Surgery kit. The device is CE marked and used within its intended use. Minimal risks are expected for subjects participating in the current study.

Treatment and rehabilitation will not differ significantly for participating research subjects

CONFIDENTIAL

compared to patients undergoing a BAHS procedure outside the study. The implants and abutments are CE-marked, thus identical to the ones used in a regular surgery. The surgical technique used in the study (MONO technique) is a further development of the MIPS technique. It is a simplified technique utilizing one drilling step in contrast to the three-step drilling procedure used today. The drill depth with the MONO drill together with the Cannula is 4.75 mm, which is 0.15–0.2 mm less deep than the surgical techniques used today when drilling for a 4 mm implant – the far most common implant used for adults. By using a one-step drilling procedure, the need for drill hole alignment is eliminated. Tests have also shown minimal heat generation during drilling when used according to instructions. Furthermore, less discomfort for the patient is expected since the drilling procedure is performed in one step rather than three.

Post-operative procedures are the same for participating research subjects compared to patients undergoing a BAHS procedure outside the study, thus not contributing to any additional risk. The only exceptions from the routine procedure are the use of a patient questionnaire (see section 10.3.9), which will extend the duration of one of the visits, and one to three additional visit(s) after surgery (vary between investigation sites).

Per above, participation in the study will result in a higher frequency and duration of follow-up visits. This will require an extra effort for the subject. On the other hand, the subject will have the opportunity to interact more with the treating physician and other relevant personnel, which by some may be considered as advantageous. Treatment of possible complications for study subjects will be the same as for regular implant patients. All adverse events will be registered and taken into consideration when compiling the final report. For information about anticipated adverse device effects (ADEs), see section Complications in the Surgical Manual.

Subjects enrolled may not personally benefit from participating in this study, but the knowledge and experiences gathered may lead to development of safer and more efficient BAHS products and surgical procedures for others.

7.1 Residual risks and Anticipated adverse device effects

Risk management process to identify and manage risks according to ISO 14971:2019 has been implemented covering the whole life cycle of the MONO Surgery kit. Qualitative and quantitative aspects of clinical safety of risks have been examined and documented as part of the process. The identified risks have been mitigated as far as possible and all residual risks are anticipated to be acceptable (according to the Sponsor's risk acceptability criteria). Anticipated adverse device effects as a result of the residual risks are summarized below.

7.1.1 Risks associated with use of the Ponto system

Patients who meet the indications for implantation should be informed about typical risks associated with surgery (effects from general anesthesia, infections, etc.), which are independent of the product itself. This also includes temporary numbness and/or pain that could occur during the healing period.

Serious complications during surgery (e.g. heavy bleeding (not controlled using standard hospital practice), epidural hematoma, intracranial injury) are rare, but should be carefully considered. No reports of the mentioned complications have so far been identified through the company's Post Market Surveillance.

Explantation may be required e.g. in the following cases: device failure (e.g. caused by head trauma), medical or surgical complication (persistent skin infection), need of radiation therapy, or

deterioration of hearing (outside of indicated use). Often, but not always, the abutment alone can be removed, leaving the implant in position under the skin; this is in most cases a minor procedure and requires no additional surgery.

Harm associated with the implant surgery (such as persistent numbness and/or pain) and use, (such as skin overgrowth) are accounted for in the risk analysis. These risks have been evaluated, and the materials and design of the implant have been chosen to minimize these risks.

Minor infections may occur in the area of the percutaneous abutment during use and are often handled by local treatment (hygienic recommendations to avoid local infections are made in the Surgical Manual).

The use of the sound processor carries low risks (typically temporary discomfort or that the patient is unaided if e.g. the device malfunctions). Hazardous situations can however occur, e.g. if a battery is swallowed and leakage of the content occurs. These risks have been mitigated as far as possible by design of the sound processor.

In summary, the risks identified in the risk management process are typical for percutaneous implant systems. Similar systems have been on the market for several years without any reports of major complications. All identified risks have been reduced as far as possible and all residual risks are anticipated to be acceptable (according to the company's risk acceptability criteria) and outweighed by the medical benefits of the Ponto bone anchored hearing system.

7.1.2 Risks associated with the MONO Surgery kit

No new risks are anticipated with the MONO Surgery kit or the MONO surgical procedure, in addition to those identified above. However, probability of harm could differ.

All individual residual risks are anticipated to be acceptable (according to the company's risk acceptability criteria). No clinical data on the final design of the system under evaluation has been generated and the residual risk assessment is therefore based on state-of-the-art (including equivalent and bench-mark systems) as well as expert opinions.

7.2 Anticipated clinical benefits

7.2.1 Expected benefits with the Ponto system

Claims on clinical benefit:

- Improved ability to hear sounds
- Improved speech intelligibility
- Improved quality of life

7.2.2 Expected benefits with the MONO Surgery kit

The MONO Surgery kit is an accessory to the Ponto implant and part of the Ponto system and does not have a patient benefit in itself. However, a fully functional percutaneous "implant/abutment complex" is a prerequisite for the patient to have benefit of the Ponto system. Therefore, the indirect intended benefit of the MONO Surgery kit is here defined as that it provides a fully functional implant/abutment complex installation allowing loading and use of the sound processor (see section 10.3.1).

7.3 Risks associated with participation in the clinical investigation

The MONO Surgery kit will be used for implantation of Ponto implants by experienced ENT specialists with knowledge and training ensuring appropriate patient recruitment, effective patient

oticon MEDICAL	Title BC108 CIP MONO	Document no Doc-00068506	Revision 2	Page 19(48)
--------------------------	--------------------------------	------------------------------------	----------------------	-----------------------

care and follow-up. All ENT specialists involved in the investigation are experienced in both the linear incision technique with tissue preservation and the MIPS technique, and will also receive training in the MONO surgical procedure and use of the MONO Surgery kit prior to initiation of the investigation.

The MONO Surgery kit is CE-marked and has been tested for reliability and biocompatibility to ensure the design of a reliable and safe product. Therefore, no additional risks other than those described in section 7.1 are expected due to participation in the investigation.

All participants in the investigation will attend frequent follow-up visits to monitor safety and performance of the Ponto implant/abutment complex installed by using the MONO surgical procedure. This will allow for the detection of any complications at an early stage and the possibility to take appropriate action. The subjects will have the opportunity to frequently interact with the treating physician and the assessments performed in the visits are non-invasive and closely follows clinical practice. All procedures, investigations and outcome measures in the clinical investigation are standard methods used in the field of BAHS research, and there are no assessments in the investigation that add additional risks to the patients.

7.4 Possible interactions with concomitant medical treatments

During surgery, no risks in relation to concomitant medication other than those associated with surgery in general (e.g. use of anticoagulants) are anticipated.

During the clinical investigation, medication which is considered necessary for the patient's safety and well-being may be given at the discretion of the investigator. The administration of this medication and all medication for adverse events must be recorded in the appropriate section of the electronic Case Report Form (eCRF).

7.5 Risk control and/or mitigation

The identified risks have been mitigated as far as possible through verified design considerations, process validation and information and warnings in instructions for use. All individual residual risks are acceptable (according to the manufacturer's risk acceptability criteria).

7.6 Risk-to-benefit rationale

Potential hazards associated with the implantation and use of the MONO Surgery kit have been through a comprehensive risk management process in accordance with ISO 14971. Overall, the residual risks associated with the use of the MONO Surgery kit are of low severity and comparable to similar products on the market when the system is used as intended.

Furthermore, this investigation has been designed to minimize the risks as far as possible. The inclusion of patients has been limited to only adults and the inclusion and exclusion criteria have been set to exclude patients with expected bone thickness less than 5 mm, or concomitant medical conditions that could increase the risk associated with investigation participation to unacceptable levels. No procedures or assessments in the investigation add additional risks to the patients. The investigation will be performed in accordance with applicable rules and regulations, and follow ethical and scientific standards for designing, conducting, recording and reporting clinical studies to ensure that the rights, safety and wellbeing of the participating patients are protected.

It is concluded that the benefits associated with implantation, e.g. by using the MONO Surgery kit, outweigh the overall residual risks. Furthermore, it is concluded that the anticipated risks associated with participation in the investigation are acceptable when weighted against the anticipated user benefits of participation.

CONFIDENTIAL

8 OBJECTIVES AND ENDPOINTS

8.1 Primary objective

Primary objective	Corresponding primary endpoint/outcome variable(s)	Section
A. To investigate the proportion of Ponto implant/abutment complexes providing a reliable anchorage for a sound processor three months after MONO surgical procedure	1. Composite variable [Yes/No] including: I. Implant/abutment complex in situ II. Implant stability III. Absence of: a. Holgers score ≥ 2 , preventing use of sound processor b. Patient-reported pain preventing use of sound processor c. Skin overgrowth preventing use of sound processor	10.3.1

8.2 Secondary objective(s)

Secondary objective(s)	Corresponding secondary endpoint/outcome variable(s)	Section
B. To investigate the proportion of Ponto implant/abutment complexes providing a reliable anchorage for a sound processor after MONO surgical procedure	1. Composite variable [Yes/No] to be assessed at 6- and 12 months post-surgery including: I. Implant/abutment complex in situ II. Implant stability III. Absence of: a. Holgers score ≥ 2 , preventing use of sound processor b. Patient-reported pain preventing use of sound processor c. Skin overgrowth preventing use of sound processor	10.3.1
C. To investigate the rate of implant survival	1. Implant in situ [Yes/No] assessed at 9 days, 5 weeks, 3-, 6- and 12 months post-surgery	10.3.2
D. To investigate the rate of implant perceived as stable	1. Implant stability [Yes/No] assessed at 9 days, 5 weeks, 3-, 6- and 12 months post-surgery	10.3.3
E. To assess the skin condition around the abutment	1. Holgers score (scale 0–4) assigned by investigator at 9 days, 5 weeks, 3-, 6- and 12 months post-surgery 2. Max Holgers score per patient during 0–3 months and 0–12 months post-surgery 3. Mild/Adverse skin reaction per patient during 0–3 months and 0–12 months post-surgery (adverse skin reaction defined as Holgers ≥ 2 on at least one follow-up visit)	10.3.4.2

	including unplanned visits during the analysis period)	
4.	Total and individual IPS scores (scale I: 0–4; P: 0–2; S: 0–2) assigned by investigator at 9 days, 5 weeks, 3-, 6- and 12 months post-surgery	10.3.4.3
5.	Wound healing [Yes/No] assessed at 9 days, 5 weeks, 3-, 6- and 12 months post-surgery	10.3.4.1
6.	Dehiscence [Yes/No] measured at the widest point [millimetres] at 9 days, 5 weeks, 3-, 6- and 12 months post-surgery	10.3.5
7.	Skin overgrowth [Yes/No] assessed at 9 days, 5 weeks, 3-, 6- and 12 months post-surgery	10.3.4.3
F.	To investigate post-operative events around the abutment	1. Post-operative events assessed at 9 days, 5 weeks, 3-, 6- and 12 months post-surgery
G.	To investigate patient-perceived pain around the abutment	1. Assessment of presence [Yes/No] and magnitude (scale 0–10) of patient-perceived pain at 9 days, 5 weeks, 3-, 6- and 12 months post-surgery
H.	To investigate patient-perceived numbness around the abutment	1. Assessment of presence [Yes/No] and magnitude (scale 0–10) of patient-perceived numbness at 9 days, 5 weeks, 3-, 6- and 12 months post-surgery
I.	To evaluate duration of surgery	1. Length of surgery [minutes] from punch to placement of healing cap
J.	To investigate sound processor usage by patients	1. Average sound processor usage time [hours per day; days per week] at (5 weeks), 3, 6 and 12 months
K.	To investigate patient-reported benefit after surgery	1. Glasgow Benefit Inventory (GBI) benefit scores as for total-, general-, social- and physical scores at 3 months

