Following screening and surgery, subjects will come for post-operative follow-up visits at 9 days*, 5 weeks*, 3 months, 6 months, and 12 months following implant installation. With some minor deviations, it is routine clinical practice for patients to visit the clinic at these intervals for follow-up. At each visit, a clinical evaluation of the surgical site and implant will be made, and a range of outcome measures related to implant, skin status and post-operative events are collected. Sound processor fitting/implant loading will be scheduled according to local clinical practice, which may vary across study sites and may fall outside the data collection visit intervals defined in this protocol. If the loading visit constitutes an additional follow-up not accounted for in the schedule, the study participant will be screened for adverse events and referred immediately for physical examination if necessary. At all visits, study participants will be screened for adverse events and referred immediately for physical examination if necessary.

*Will vary between the study sites, depending on their normal follow-up schedules.

All clinical and investigation-related data will be recorded in eCRFs. A schematic overview of the investigation visits and collected variables is shown in Table 4.

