9.1.1 Clinical Investigation flow chart

Table 4. Flow chart of the investigation

Protocol activity	V1	V2	V3	V4	V5	V6	V7	Un-scheduled visit(s)
	Screening	Surgery	Surgical follow-up	Follow-up	Follow-up (Primary endpoint)	Follow-up	Follow-up (End of study)	
	Pre-surgery	0	9 days	5 weeks**	3 months	6 months	12 months	
			± 3 days	± 2 weeks	± 1 week	± 2 weeks	± 1 month	
Subject Eligibility								
Informed consent	X							
Inclusion/exclusion criteria	X	X						
Baseline characteristics	X							
Medical and surgical history	X							
Audiology								
Fitting Sound Processor*				X	X			
Implantation								
Surgical information		X						
Intra-operative events		X						
Post-operative assessment								
Post-operative events			X	X	X	X	X	X
Skin assessments			X	X	X	X	X	X
Implant survival			X	X	X	X	X	X
Manual implant stability			X	X	X	X	X	X
Subjective pain and numbness assessment	X		X	X	X	X	X	X
Sound processor usage				(X)	X	X	X	
PRO's								
GBI					X			
Safety								
Adverse events assessment		X	X	X	X	X	X	(X)

* Sound processor fitting will occur according to local clinical practice, but no later than at the 3-month follow-up visit.

** The extended visit window is due to different local clinical practices regarding post-operative follow-up.

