10.3.6 Pain assessment

The patient is asked if pain around the abutment is present [No/Yes].

If pain is present [=Yes]:

- Magnitude will be recorded using an NRS [scale from 0 = no pain to 10 = worst imaginable pain].
- Subject will also be asked if perceived level of pain prevents use of the sound processor [No/Yes], if applicable.
- Subject will be asked if pain increases with manipulation of the abutment [No/Yes]

If pain is not present [=No]:

- NRS score of 0, [0 = no pain] will be implicit.

CONFIDENTIAL

oticon MEDICAL	Title BC108 CIP MONO	Document no Doc-00068506	Revision 2	Page 33(48)
--------------------------	--------------------------------	------------------------------------	----------------------	-----------------------

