19.3 Reporting of Adverse Event(s)

All health problems*, whether judged as related to the surgery and/or the Ponto products or not, that are reported by the subject, found in medical records or found at the clinic visits must be recorded by the PI, or authorised designee, in the eCRF as an AE, preferably within 5 working days. For events judged as related, i.e. ADEs, additional information is required as specified in eCRF.

**except those defined and excluded from the investigation.*

19.3.1 *Reporting of Serious Adverse Event / (Unanticipated) Serious Adverse Device Effect*

In addition to the information already collected and recorded for AEs/ADEs, there are more detailed information required for SAEs/SADEs/USADEs as specified in eCRF.

For SAEs/SADEs/USADEs the Investigator must:

- Record SAE/SADE/USADEs details in the eCRF immediately, but no later than **24 hours** after becoming aware of the event. An email to Oticon Medical will automatically be generated by the EDC system after investigator signing of the SAE form by the Investigator. In addition, an email shall be sent to responsible clinical trial manager (to notify the SAE/SADE/USADE).
- Follow up the initial SAE/SADE/USADEs information as soon as new information is available.
- Report SAE/SADE/USADEs to the EC according to local requirements (e.g. per event and/or annually). In multicentre investigations this may include the SAE/SADE/USADEs reported from another site; this information will be provided by Oticon Medical, if required.
- Provide Oticon Medical with all SAE/SADE/USADEs related documentation and correspondence to the EC.

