19.4 Non-reportable events

When performing a BAHS surgery, some intra- and post-operative events are more or less likely to occur (i.e. not 'untoward' per se) (see sections 10.2.3 and 10.3.5). Therefore, in this investigation, the following events will be captured in the eCRF on the applicable study visit. To avoid double-reporting, these events will not be recorded in the AE log, unless the investigator judges them to exceed the level of what is to be expected (i.e. 'untoward' per se):

During surgery;

- Drilling into veins
- Drilling into air pockets
- Dura mater exposed

Post-operative complications

- Bleeding or hematoma
- Pain or numbness
- Skin dehiscence
- Erythema
- Edema
- Granulation tissue
- Skin reactions
- Revision surgery

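### Section 19.4 exempts expected skin reactions and pain from the AE log even when no visit form has scored them, so some between-visit episodes reach neither the period Holgers summaries nor the AE tables

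*Combined protocol and SAP*

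**What the plan says.** **Skin and pain scoring.** Section 8.2, objective E, summarises the maximum Holgers score (E.2) and mild/adverse skin reaction (E.3) per patient over 0–3 and 0–12 months. E.3 is "adverse skin reaction defined as Holgers ≥ 2 on at least one follow-up visit", and section 8.2 adds "including unplanned visits during the analysis period". The synopsis gives the same definition without that addition. Table 4 (section 9.1.1) marks skin, pain and post-operative event assessments at unscheduled visits as well as scheduled ones. On pain, section 10.3.6 reads: "The patient is asked if pain around the abutment is present". Neither the Holgers item nor the pain item has a recall period.

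**Adverse events.** Section 10.4 has sites ask at every visit about health problems since the previous one. Section 19.3 requires problems reported by the subject or found in medical records to be entered as AEs, "except those defined and excluded from the investigation". Section 19.4 lists the exempted events, among them bleeding, pain, erythema, edema, granulation tissue and skin reactions. It says they are captured on the relevant visit form and continues: "To avoid double-reporting, these events will not be recorded in the AE log, unless the investigator judges them to exceed the level" to be expected.

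**The concern.** The exemption in 19.4 rests on avoiding a second record of something the visit form already holds. That reason fails for an episode that was never on a visit form. Holgers, IPS and pain describe the site on the visit day, and the one question that looks back over the interval feeds a reporting duty from which these same events are carved out.

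The affected outputs are presented as period measures: E.2 and E.3 over 0–3 and 0–12 months, and the related-AE summary at 3 and 12 months (sections 8.3 and 10.4). Section 6.1 calls skin reactions the most common complication, so these are the rates a reader of the report will look for. After month 3 the scheduled visits are three and six months apart.

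**Working it through.** **Step 1: follow one episode through the plan.** Suppose the site becomes moist and swollen in month 9, is treated by a family doctor, clears, and the patient mentions it at the 12-month visit.

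- Visit form: Holgers (10.3.4.2) grades the site as it is now, so the score is 0. The pain question is answered No. The IPS pain item (10.3.4.3) has a duration element, but only for pain still present.
- Unplanned visit: none took place, so the clause in 8.2 does not apply.
- Interval question (10.4): the patient reports the episode. The duty to record in 19.3 is lifted for events listed in 19.4, and skin reactions are listed.
- Investigator's judgement (19.4): if the episode is judged to exceed the expected level it is logged. If not, it stays out.
- Medication (10.3.10): the eCRF takes drugs given at the investigator's discretion and drugs given for AEs. An entry may exist, but no endpoint or table counts it.

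An episode judged expected therefore adds nothing to E.2, E.3 or the related-AE tables. No section limits the exemption to events actually scored on a form.

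**Step 2: how often would a scheduled visit see an episode?** The plan gives no figure for this. Its only computed figures are the sample size and interval widths in section 12.2, which do not enter here. (A Wald calculation gives 4 × 1.96² × 0.85 × 0.15 / 0.20² = 48.98, or 49, against the stated 50.)

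Inputs: visits at 9 days, 5 weeks, 3, 6 and 12 months (section 9.1), taken as days 9, 35, 91, 182 and 365. Assumptions not in the documents: one episode per affected patient, onset uniform over the period T, and duration d of 7, 14 or 28 days.

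An episode with onset x is seen if some visit v satisfies x ≤ v ≤ x + d. The share seen, s, is the total length of the onset windows from max(0, v − d) to v, counted once where they overlap, divided by T.

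| d | 0–3 months (T = 91) | 0–12 months (T = 365) |
|---|---|---|
| 7 days | (7+7+7)/91 = 21/91 = 23% | (5×7)/365 = 35/365 = 10% |
| 14 days | (9+14+14)/91 = 37/91 = 41% | (9+4×14)/365 = 65/365 = 18% |
| 28 days | (35+28)/91 = 63/91 = 69% | (35+3×28)/365 = 119/365 = 33% |

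**Step 3: add unplanned visits.** Let u be the share of episodes missed at scheduled visits that prompt an unplanned study visit. The share captured for E.3 is s + (1 − s)u. For a true 12-month patient rate of 15%, used purely as an illustration, the observed rate is 15% × [s + (1 − s)u]:

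| u | 7 days | 14 days | 28 days |
|---|---|---|---|
| 0 | 1.4% | 2.7% | 4.9% |
| 0.5 | 8.2% | 8.8% | 9.9% |
| 0.8 | 12.3% | 12.5% | 13.0% |
| 1 | 15% | 15% | 15% |

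The plan states neither d nor u, so the result runs from no loss to most of the rate.

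**The case against.** The strongest defence has four parts.

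- **Unplanned visits count.** A patient whose reaction brings them back to the clinic is scored under 8.2 and Table 4. This stands, and it may recover most episodes. It cannot reach those that are self-managed or treated elsewhere.
- **The exemption is conditional.** An episode needing outside treatment nine months after surgery could well be judged untoward and logged. This also stands, but it depends on judgement. Section 6.1 describes local treatment as typical for Holgers 2, and section 7.1.1 describes minor infections as often handled locally, so a routine treated reaction can readily be judged expected. An AE entry also does not bring the episode into E.2 or E.3.
- **The exemption presupposes capture on a form.** That is a natural reading of its purpose, but the text does not make capture a condition.
- **Visit-scored Holgers is an openly defined endpoint.** True, which is why E.3 itself should not be redefined.

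The scope is also limited. Pain and IPS are reported by visit, as point prevalences, and are not biased by this. For pain only the related-AE tables are exposed. Bleeding is recorded under section 10.3.5, which states no recall period but does not confine the item to what is visible that day, so its position is unclear rather than plainly deficient.

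A reader might infer three stronger things that the documents do not support. One is that between-visit episodes are counted nowhere: untoward ones are logged, and medication may leave a trace. Another is a shift of 4 to 6 points, from two or three patients missed in 50 (2/50 and 3/50): that count depends on u, which is not stated. The third is that MONO would look better than published results. The 15% of patients in section 6.1 is reported beside 5% of visits and may itself be visit-scored, and the study has no comparator.

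**Conclusion.** The gap is real and narrow. It needs three conditions together: the episode resolves between visits, it prompts no unplanned study visit, and the investigator judges it within the expected level. Such an episode is absent from E.2, E.3 and the related-AE tables even when the site knows about it. The direction is certain for the 0–3 and 0–12 month summaries, which can only be too low through this route. The size is not derivable: the percentages rest on assumed durations, uniform onset, nominal visit days and one episode per affected patient, and the unplanned-visit share is unknown. By-visit rates, the 3-month primary endpoint and the sample size are untouched. It deserves correction because the remedy is small and the affected rates concern the most common complication.

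**What to change.** - In section 19.4, limit the exemption to events actually scored on a planned or unplanned visit form. An implant-site skin reaction, pain or bleeding reported for the time between visits, and not scored on a form, is then recorded as an AE with dates and any treatment.
- Label E.2 and E.3 as observed at planned and unplanned visits. The SAP that section 12.3 calls for can carry this.
- Report treated between-visit skin reactions as a separate descriptive row beside E.3, leaving E.3 unchanged, since no Holgers grade was assigned to them.
- Align the synopsis definition with the unplanned-visit clause in section 8.2.

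The cost is one sentence in 19.4, a label, a table row and a synopsis edit. The downside is some additional AE entries and a slightly higher reported complication count.
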